8.1 General Conventions

All statistical analyses will be performed using SAS® Version 9.4 or higher, unless otherwise noted. Standard descriptive summaries for continuous data include the number of subjects with non-missing observations (n), mean, standard deviation (SD), median, minimum, and maximum values. For categorical data, the count and percentage will be provided. Percentages will be based on the number of subjects without missing data. If exploratory tests of hypotheses are performed, t-tests will be performed for continuous variables, and Fishers' Exact Test will be performed for categorical variables. Baseline for the Forgotten Joint Score is 6 weeks. Baseline for all other endpoints is the pre-operative

measurements collected before surgery. Unless specifically stated otherwise, all endpoints will be analyzed first by treatment then combined.

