10.3 Levels of Significance

The level of significance for the hypotheses related to the non-inferiority/superiority tests of the primary endpoint and for the hypotheses associated with the secondary endpoints is defined is sections 10.9.2 and 10.9.3.

Unless otherwise stated, all other confidence intervals and p-values will be provided for exploratory analyses to facilitate clinical judgement, with no adjustment of significance levels; Confidence intervals will be 2-sided 95% confidence intervals.

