In addition, the following secondary endpoints do not have prospectively planned hypotheses; these will be summarized for both treatment groups:

- Harris Hip Score (HHS) and HHS change from preoperative baseline
- Forgotten Joint Score (FJS) and FJS change from 6-week postoperative baseline
- EQ-5D-5L and changes in these assessments from preoperative baseline
- Pain (Groin, Thigh, and Buttock)
- Patient Satisfaction
- Post-op time when functional activities can be accomplished (return to work; self-care; etc.)
- Radiographic Outcomes (based upon: AP Hip, AP Pelvis, and Lateral)
- Length of hospital stay after index THA
- Re-hospitalizations during the study (including a specific summary of re-hospitalizations within 90 days)
- Narcotic drug usage throughout the study (patient reported)
- Complications (including a specific summary of complications within 90 days post-surgery)

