10.9.4 Secondary Endpoints

All secondary endpoint analyses will be performed on the Per Protocol Population.

Skin-to-skin OR time in minutes will be summarized as a continuous endpoint for both treatments. The difference in means $\mu_I - \mu_C$ will also be summarized as a continuous endpoint. Its 1-sided upper 95% confidence limit and the p-value for the test of non-inferiority with a margin of 3.75 based on a 2-sample t-test will be produced if the alternative hypothesis of non-inferiority of the primary endpoint is rejected.

The difference between acetabular cup abduction angle and plan for each subject will be summarized as a continuous endpoint for both treatments. The proportion of subjects with acetabular cup abduction angle within 10% of plan will be summarized as a categorical endpoint for both treatments. The difference in proportions $P_I - P_C$ will also be summarized as a categorical endpoint. Its 1-sided lower 95% confidence limit and the p-value for the test of non-inferiority with a margin of 10% based upon a normal approximation method will be produced if the alternative hypothesis of non-inferiority of skinto-skin OR time is rejected.

The difference between acetabular cup version angle and plan for each subject will be summarized as a continuous endpoint for both treatments. The proportion of subjects with acetabular cup version angle within 10% of plan will be summarized as a categorical endpoint for both treatments. The difference in proportions $P_I - P_C$ will also be summarized as a categorical endpoint. Its 1-sided lower 95% confidence limit and the p-value for the test of non-inferiority with a margin of 10% based upon a normal approximation method will be produced if the alternative hypothesis of non-inferiority of acetabular cup abduction angle within 10% of plan is rejected.

With no prospectively planned hypotheses, the following secondary endpoints will be summarized at all visits with available data for both treatments as continuous variables:

- The Harris Hip Score (HHS) and change from baseline HHS
- Forgotten Joint Score (FJS) and change from 6-week postoperative FJS
- EQ-5D-5L and change from baseline
- Pain (Groin, Thigh, and Buttock)
- Patient Satisfaction
- Radiographic Outcomes (based upon: AP Hip, AP Pelvis, and Lateral)
- Length of hospital stay after index THA

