Sticker sheets were created, one set for up to 30 sites, containing treatment assignments for 120 subjects using a fixed block size of 4 and a treatment allocation ratio of 1:1. On the face of each sticker is a character in the sequence A, B, C,, X, Y, Z, AA, AB, AC,AX, AY, AZ, BA, BB, BC, etc...., BX, BY, BZ, CA, etc...

The stickers should be removed sequentially to reveal the randomization code and treatment group ('Study (Kincise)' or 'Control (Mallet)') for each consecutive consented subject that meets eligibility criteria. Peeled sticker should be placed on the screening log to document that randomization was unbiased. The planned randomization group should then be documented in the applicable source document and on the Randomization eCRF (eCRF RDM) in the database.

The assigned treatment will remain secret to site personnel until subject is found to meet all eligibility criteria; No other blinding is implemented in this study.

4 Interval Windows

The study includes the following periods: Pre-op, Operative, Immediate post-op, 6 Week, 24 Week. Intervals related to each are shown in Table 3, below.

Visit	Minimum Day	Maximum Day	Midpoint Day
Pre-Op	-180	0	
Operative	0	0	0
Immediate post-op	0	Discharge	
6 week	14	60	37
24 week	61	200	130

 Table 3
 Interval Windows for Non-Radiographic Study Visits

Time point specific data collected to satisfy the primary and secondary efficacy-related objectives will be assessed for compliance with these intervals. Only data which can be attributed to the visit intervals in Table 3 will be used in the analysis of primary and secondary endpoints. This visit will be hereafter referred to as the Analysis Visit and the originally recorded visit as the Nominal Visit. If multiple measurements fall into the pre-operative window, or into the 'Immediate post-op' post-operative window, the result collected most proximate to surgery will be utilized. For the '6 week' and '24 week' visits, if multiple measurements fall into the window will be utilized for analysis.

5 Levels of Significance

The level of significance is 95%. Primary endpoint analyses, further described in section 8.7, and secondary endpoint analyses with hypotheses, further described in 8.8, will use 1-sided 95% confidence intervals and associated p-values. Data summaries of secondary endpoints without hypotheses and of exploratory endpoints will use 2-sided 95% confidence intervals and associated p-values.

6 Analysis Sets

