8.8.8 Hip Evaluation at Pre-op, 6 week, 24 week

All questions on the Pre-op hip evaluation CRF will be summarized: ("How satisfied do you anticipate you will be with this procedure?", "Groin pain", "Buttock pain", "Leg length", "Can you walk without an aid?", "Do you drive?", "Can you perform basic activities of daily living (bathing, getting in and out of bed, etc)?", "Can you perform light household duties? (cooking, dusting, etc.)", "Can you perform moderate/heavy household duties (cleaning floors, moving heavy boxes, etc.)?", "Can you go up and down a flight of stairs using a handrail?", "Can you put on socks/stockings without someone's assistance?", "Can you bend down to pick up an object on the floor?", "Can you stand up from a chair without assistance?", "Con you work?") as categorical data using the Per Protocol Analysis Set.

All questions on the Post-op hip evaluation CRF will be summarized: "How satisfied are you with this procedure?", "Would you have this procedure again?", "Groin pain", "Buttock pain", "Leg length", "How long did you take narcotics after your surgery?") as categorical data using the Per Protocol Analysis Set.

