8.8.9 Hip Evaluation Functional Recovery Outcomes

All questions on the hip evaluation functional recovery outcomes will be summarized as categorical data using the Per Protocol Analysis Set in the following fashion: recovery time will be the first week (Week 1 – After Week 12) recovery was achieved; Otherwise, recovery time will be "Still cannot do" or "Not Applicable/I never do this" if subject selected these options at the last visit subject was seen.

8.8.10 Radiographic Outcomes (based upon: AP Hip, AP Pelvis, and Lateral) at week 6, week 24

The following radiographic endpoints will be summarized at week 6 and at week 24: Acetabular cup version – Hip, Acetabular cup version – Pervis, Acetabular cup Inclination, Acetabular cup migration, Acetabular cup radiolucency, Acetabular cup osteolysis, Acetabular cup scerotic lines, Acetabular cup porous coating integrity, Femoral stem position, Femoral stem tilt, Femoral stem subsidence, Femoral stem radiolucency, Femoral stem osteolysis, Femoral stem osteolytic lines, Femoral stem coating integrity, Calcar resorption, Calcar fracture, Heterotopic ossification, Proximal femur, Pelvis vertical alignment, Device/anatomy condition.

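### If exploratory p-values are produced, SAP 8.1 applies Fisher's exact test to ordered responses such as pain, satisfaction and week of recovery; an order-respecting method should be named instead

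*SAP*

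**What the plan says.** SAP 8.1 (General Conventions) sets the default tests in one sentence: "If exploratory tests of hypotheses are performed, t-tests will be performed for continuous variables, and Fishers' Exact Test will be performed for categorical variables". The part that matters here, that Fisher's "Exact Test will be performed for categorical variables", makes no separate provision for ordered categories.

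SAP 8.8.8 summarises the hip evaluation questions, including satisfaction, groin pain, buttock pain and how long narcotics were taken, "as categorical data using the Per Protocol Analysis Set". SAP 8.8.9 does the same for recovery: "All questions on the hip evaluation functional recovery outcomes will be summarized as categorical data using the Per Protocol Analysis Set". There the value is the first week in which an activity was regained, from week 1 to after week 12. Failing that, it is 'Still cannot do' or 'Not Applicable', as answered at the last visit attended.

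The status of these endpoints is clear. Protocol 10.5.2 states that "the following secondary endpoints do not have prospectively planned hypotheses; these will be summarized for both treatment groups". On p-values, SAP section 5 says that summaries of secondary endpoints without hypotheses and of "exploratory endpoints will use 2-sided 95% confidence intervals and associated p-values". Protocol 10.3 adds that "all other confidence intervals and p-values will be provided for exploratory analyses to facilitate clinical judgement, with no adjustment of significance levels".

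The two documents differ on data type for some of the outcomes. Protocol 10.9.4 lists pain and satisfaction among endpoints that "will be summarized at all visits with available data for both treatments as continuous variables". It lists time to functional activities and narcotic use as categorical, as the SAP does.

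**The concern.** A test on an r × 2 table that treats the levels as labels returns the same p-value if the levels are shuffled. For pain, satisfaction or recovery week, a difference between arms would most plausibly be a shift along the scale, and an unordered test is weak against that pattern because it spreads its sensitivity over every possible departure. Nor does Fisher's test on more than two levels yield a single between-arm effect estimate or interval, although SAP section 5 speaks of intervals alongside p-values.

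At stake is the reading of the patient-facing comparison. A non-significant Fisher p-value could be taken as evidence of no difference when the test had little chance of showing one. Switching to an ordinal test after seeing the data would be post hoc.

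**Working it through.** **Plan figures.** The documents give no power, effect size or number of response levels for these outcomes, so there is no stated figure to reproduce on this point. Their power statements concern the formal endpoints only. As a check on one of these, the primary non-inferiority N is 2 × (1.645 + 1.645)² × (2.5/1.25)² = 2 × 10.82 × 4 = 86.6, so 87 per group by normal approximation. With the t distribution, 88 per group gives 95.1% power, matching the stated 88. Nothing below touches it.

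**Inputs.** From the documents: two-sided 5% level (SAP section 5) and 200 per group (SAP section 7). Assumed: an effect giving an order-using test 80% power; a consistent shift across levels; 3, 4 or 5 levels for pain and satisfaction; and 13 or 14 levels for recovery if weeks are recorded singly (weeks 1 to 12 and after week 12 make 13; adding 'Still cannot do' makes 14).

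**Step 1, noncentrality.** An order-using test spends 1 degree of freedom. For 80% power, λ = (1.960 + 0.842)² = 7.85.

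**Step 2, same signal, order ignored.** With k levels the unordered test has k − 1 degrees of freedom. In large samples its power is the probability that a noncentral chi-square with k − 1 df and λ = 7.85 exceeds the 5% critical value.

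| Levels | df | Power |
|---|---|---|
| 2 | 1 | 80.0% |
| 3 | 2 | 70.9% |
| 4 | 3 | 64.5% |
| 5 | 4 | 59.5% |
| 13 | 12 | 39.4% |
| 14 | 13 | 37.9% |

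**Step 3, simulation with the exact test itself.** 200 per group, proportional-odds shift, 1,500 trials per row, Monte Carlo r × 2 Fisher (Freeman–Halton) test. The odds ratio in each row was tuned to give Wilcoxon about 80%. Simulation error is at most √(0.25/1500) = 1.3 percentage points per entry.

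| Levels (frequencies) | Odds ratio | Wilcoxon | Fisher |
|---|---|---|---|
| 3 (equal) | 1.68 | 79.4% | 69.4% |
| 4 (equal) | 1.66 | 80.4% | 64.9% |
| 5 (equal) | 1.63 | 78.0% | 55.0% |
| 5 (skewed) | 1.74 | 80.4% | 60.3% |
| 13 (equal) | 1.62 | 79.1% | 38.9% |
| 13 (skewed) | 1.64 | 79.5% | 37.7% |
| 14 (equal) | 1.63 | 81.0% | 37.4% |

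The exact test behaves much as the chi-square calculation predicts, so the approximation does not create the loss.

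**Step 4, is recovery week fully ordered?** Not quite. SAP section 4 allows the 6-week visit on Days 14 to 60 and the 24-week visit on Days 61 to 200. A subject last seen on Day 20 (20/7 = 2.9 weeks) or Day 65 (65/7 = 9.3 weeks) who still cannot do an activity has not been observed to Day 84 (12 × 7). Whether that subject would recover before or after someone recorded as after week 12 is unknown. Ranking every 'Still cannot do' last would treat censoring as the worst outcome. 'Not Applicable' has no place in the order at all.

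**Step 5, data type.** Under SAP 8.1, moving pain and satisfaction from continuous to categorical changes the default test from a t-test to Fisher's. SAP Table 10.1 lists two substantive changes: removal of thigh pain, and the correction of the gatekeeping wording. This reclassification is not among them.

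**The case against.** The strongest reply is that no test of these outcomes is firmly planned. SAP 8.1 begins with a condition, the endpoints have no hypotheses, and SAP 8.8.8 and 8.8.9 speak only of summaries. A reader might infer that the plan commits to Fisher's test for every ordered outcome, and the documents do not support that. What remains is that SAP section 5 says without condition that such summaries will carry p-values, and Fisher's is the only test named for categorical data.

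A reader might also infer that the SAP threw away order that the protocol used throughout. That holds only for pain and satisfaction. Recovery time and narcotic use were already categorical in Protocol 10.9.4, and recovery time is the outcome behind the largest loss.

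The power figures depend on assumptions: the 80% start, the level counts, and a consistent shift, which favours a rank test. With 3 or 4 levels the loss is moderate. This stands, and it is why a range is shown.

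On intervals, section 5 could be met by an interval for each arm's percentage at each level. That is fair, but it still leaves no estimate of the difference between arms across the scale.

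**Conclusion.** The point holds in conditional form and is minor to moderate. If exploratory p-values are produced, the SAP's default for ordered responses ignores their order and supplies no between-arm effect estimate. Against a consistent shift with 80% power for an order-using test, power falls to 70.9%, 64.5% or 59.5% with 3, 4 or 5 levels. It falls to 37.9% with 14 levels, on the further assumption that recovery weeks are recorded singly and can be fully ordered, which Step 4 shows is only approximately so.

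It would be wrong to conclude that the trial itself loses power. Study success rests on broaching time, the gatekept tests concern operating time and cup angles, and none of these is affected.

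**What to change.** 1. **SAP 8.1.** Restrict Fisher's exact test to binary and unordered variables. For ordered responses (satisfaction, groin and buttock pain, duration of narcotic use), name the Wilcoxon rank-sum test, or the Cochran–Mantel–Haenszel row mean score test, with a proportional-odds ratio and two-sided 95% confidence interval. State whether p-values will be produced, so that 8.1 and section 5 agree.
2. **SAP 8.8.9.** For recovery week, leave 'Not Applicable' out of the comparison and report its count. Treat 'Still cannot do' as censored at the last visit attended, for example with a log-rank or interval-censored comparison, rather than ranking it last whenever the subject was last seen.
3. **SAP Table 10.1.** List the change of pain and satisfaction from continuous to categorical, with a reason.

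The cost is a few sentences, one table row and slightly more programming; no new data are needed. The odds ratio brings a proportional-odds assumption, so the counts by level should be shown beside it.

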8.2 Disposition of Study Subjects

Counts of the following categories of subjects by treatment and in total will be provided: All Enrolled dataset, Safety, major inclusion/exclusion protocol violations, Per Prototol, non inclusion/exclusion major protocol violations, deaths, withdrawals, study completion, ongoing in the study.

A subject accounting table using the Safety set will also be provided to account for the following at each follow-up interval:

- Treated: the count of subjects treated; This should not vary per visit;
- Not Yet Due: the count of subjects who do not have an evaluation at the visit (Harris Hip or Forgotten Joint) and who, based on date of surgery and date of data extract, are not yet in-window for the visit;
- Theoretical Due: the count of subjects treated and not counted in Not Yet Due;
- Death: the count of theoretical subjects who died after the start of the window and who do not have data (Harris Hip or Forgotten Joint) at the visit;
- Revision: the count of subjects theoretically due, without data at the visit, who were revised and withdrawn from the study;
- Not Yet Overdue: count of theoretical subjects within the evaluation time window;
 Do not count subjects who have data at the visit or subjects who are counted in
 Death or Revision;
- Expected: the count of subjects theoretically due who are not counted in Death, Revision, Not Yet Overdue;
- Actual data on file (records with a date): the count of subjects with a record with a date for each of the following endpoints: RSA measured subsidence, cup positioning at 6 weeks, Harris Hip, HOOS Jr., Forgotten Joint score, and Linear head penetration. A count of subjects with a record with a date in any of the listed

endpoints will also be provided and a follow-up rate will be calculated using the number of expected subjects in the interval as denominator;

- -
- Any data on file: the count of subjects with any record with a date for the endpoints listed in "Actual data on file"
- Follow-up rate calculated as 100*(Any data on file)/Expected

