7.4 Twenty-Four Week Postoperative Evaluation (Day 61 to Day 200)

The following data will be collected from twelve-week postoperative evaluation:

- Study Visit (CRF detailing type of visit and subject status)
- Postoperative Hip Evaluation (HE2)
- Postoperative Hip Evaluation Functional Outcomes (HE3*)
- Narcotic Drug Use (patient reported)
- Harris Hip Score
- Radiographs (AP Hip (unilateral), AP Pelvis (bilateral), and Lateral)

EQ-5D-5L

Confidential Version Date: 040CT2021 DePuy Synthes Protocol DSJ_2019_03 / Version 2.0 / TV-eFRM-02920

- Forgotten Joint Score
- Adverse Event Form (if needed)
- Protocol Deviation Form (if needed)
- Device Deficiency (if needed)
- End of Study (Withdrawal) Case Report Form (required unless completed previously)

* The Functional Outcomes portion of the Hip Evaluation CRF (HE3) will be initially completed at the 6 week visit, and only questions that are marked as "still cannot do" or "still have not returned to work" will be addressed at subsequent study visits

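### The assessment list and the death rule behind the SAP 8.2 follow-up rate do not fit this trial, so the rate may be misstated by about 0.25 points per affected subject

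*SAP*

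**What the plan says.** SAP 8.2 (Disposition of Study Subjects) defines a subject accounting table on the Safety set. Its elements are:

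- **Not Yet Due** is a calendar rule. It covers subjects without Harris Hip or Forgotten Joint data who, "based on date of surgery and date of data extract, are not yet in-window for the visit".
- **Theoretical Due** is everyone else treated: "Theoretical Due: the count of subjects treated and not counted in Not Yet Due".
- **Death** is "the count of theoretical subjects who died after the start of the window and who do not have data", where data means Harris Hip or Forgotten Joint.
- **Revision** removes subjects without data at the visit who were revised and withdrawn. It has no timing condition.
- **Expected** is Theoretical Due less Death, Revision and Not Yet Overdue.
- **Actual data on file** is counted for six items: "RSA measured subsidence, cup positioning at 6 weeks, Harris Hip, HOOS Jr., Forgotten Joint score, and Linear head penetration".
- **Any data on file** is "the count of subjects with any record with a date for the endpoints listed in" the row above.
- The rate is then "Follow-up rate calculated as 100*(Any data on file)/Expected".

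Protocol Table 0-1 and Sections 7.3 and 7.4 schedule the same assessments at 6 and 24 weeks: Harris Hip, FJS-12, EQ-5D-5L, the postoperative Hip Evaluation (HE2), its functional part (HE3) and films. The 24-week list includes "Radiographs (AP Hip (unilateral), AP Pelvis (bilateral), and Lateral" views. At 24 weeks HE3 asks only about items not yet resolved.

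**The concern.** The list in SAP 8.2 reads as if it belonged to a different schedule. Half of its items are not collected under any visit list in these documents, and several assessments that are collected are missing from it. The death rule treats subjects who could not have attended as missed visits, and can excuse subjects who were alive throughout a window and did not attend.

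The follow-up rate is the only completeness percentage the plan calculates. Protocol 10.4 assumes data are missing at random, SAP 8.11 imputes nothing and SAP 8.13 plans no sensitivity analysis. A reader judging the postoperative outcomes will look at this rate, so it should count what the trial collects over the subjects who could have provided it.

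**Working it through.** The documents state no expected follow-up, death or dropout rate, so there is no figure of the plan's to reproduce. The check applies the SAP 8.2 definitions literally.

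**1. Unscheduled items.** RSA subsidence, HOOS Jr. and linear head penetration are absent from Table 0-1, Protocol 7.1 to 7.4, the protocol's endpoint lists and SAP 8.8. Protocol 15.1 names the patient-completed forms as EQ-5D-5L, FJS-12 and Hip Evaluation, without HOOS Jr. SAP 8.8.10 lists stem subsidence only as an outcome from AP Hip, AP Pelvis and Lateral films. The SAP Section 10 table of substantive changes adds none of the three. Each row would show 0 of 400. Because the numerator is a union, adding three empty sets changes it by 0.

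**2. Omitted assessments.** At 24 weeks only Harris Hip and FJS-12 can enter the numerator, since cup positioning is listed for 6 weeks only. A subject with only EQ-5D-5L, Hip Evaluation or a film at 24 weeks counts as having no data, although SAP 8.8.7 to 8.8.10 summarise those data. Each such subject lowers the rate by 1/400 = 0.25 points.

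**3. Deaths before the window.** The 24-week window is Day 61 to Day 200 (SAP Section 4). A subject who dies on Day 40 becomes Theoretical Due once the calendar passes, is not in the Death row, and ends in Expected with no data.

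**4. Deaths after the window.** The Death row has no upper bound. A subject who missed the 6-week visit (Day 14 to Day 60) and died on Day 100 died after that window opened and has no 6-week data. That subject leaves the 6-week Expected count despite being alive for the whole window.

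**5. Size.** Assume 400 treated (the sample size in Protocol 3.5.3), all windows closed at extract and no revisions. The counts of subjects with data, deaths and non-attenders are assumptions.

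| Situation | As written | Corrected |
|---|---|---|
| 24 weeks, 376 with data, 2 deaths before Day 61 | 376/400 = 94.0% | 376/398 = 94.5% |
| 24 weeks, 376 with data, 4 deaths before Day 61 | 376/400 = 94.0% | 376/396 = 94.9% |
| 24 weeks, all seen, 8 with only omitted data | 392/400 = 98.0% | 400/400 = 100% |
| 24 weeks, all seen, 20 with only omitted data | 380/400 = 95.0% | 400/400 = 100% |
| 24 weeks, 40 non-attenders, 4 early deaths, 20 with only omitted data | 336/400 = 84.0% | 356/396 = 89.9% |
| 6 weeks, 376 with data, 1 non-attender dying after Day 60 | 376/399 = 94.2% | 376/400 = 94.0% |
| No such subjects | no difference | no difference |

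**6. Mismatched data checks.** Death is judged on Harris Hip or Forgotten Joint, but the numerator also accepts 6-week cup positioning. If all 400 have listed data and one of them, with only a cup film, dies in the 6-week window, that subject is in the numerator and not in Expected: 400/399 = 100.25%.

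**The case against.** The strongest reply is that little follows in practice. Harris Hip and FJS-12 are scheduled at the same visits as the omitted assessments, so few subjects may have one without the other. Defining follow-up by the two core hip scores is a defensible choice. Early deaths should be rare, since Protocol 3.3 excludes subjects with a life expectancy under 2 years, and SAP 8.2 reports deaths and withdrawals separately. Completeness can also be read for each endpoint from the n in every summary (SAP 8.1, Protocol 10.9). All of this stands and limits the size. It does not justify the text, because SAP 8.2 does not adopt a core-score definition: it names six items, three of them without a source.

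Three stronger readings are tempting, and the documents support none of them.

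- *The reported rate will be wrong.* It is wrong only if affected subjects occur, and the documents give no number. The three unscheduled items cannot move it.
- *The trial never performs those three assessments.* Protocol Section 6 refers to a separate radiographic protocol that is not among the documents. Table 0-1 is not demonstrably exhaustive either, since SAP 8.4 and 8.10 mention EMG data that it does not list. What can be said is that the three have no basis in the documents provided.
- *The trial's conclusions are at risk.* Broaching time and skin-to-skin time are measured in theatre, the tests use the Per Protocol set, and no test or analysis set is defined by this rate.

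**Conclusion.** The point holds as a mismatch between SAP 8.2 and this trial's schedule, together with a death rule that is wrong at both ends of the window. Omitted assessments and deaths before the window push the rate down. Deaths after the window, and the mismatch between the death check and the numerator, push it up. Each affected subject moves the rate by about 0.25 points when 400 are treated. The assumed counts above give gaps from 0 to about 6 points, the largest needing 20 subjects with only omitted data. Severity is low: the effect is confined to the accounting table, and the primary and gatekept secondary tests are unaffected.

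**What to change.** In SAP 8.2:

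- Replace the six items with Harris Hip, FJS-12, EQ-5D-5L, Hip Evaluation (HE2) and radiographs, at both 6 and 24 weeks.
- Let a dated HE3 record count toward any data, but give HE3 no completeness row of its own at 24 weeks. Only unresolved items are asked then, so a fully recovered attendee could appear to have no record.
- Define Death as any death up to the end of the visit window without data at that visit.
- Use one definition of data at the visit for Not Yet Due, Death, Revision, Not Yet Overdue and the numerator.

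If the separate radiographic protocol does provide for RSA or head penetration, the SAP should cite it and state the visits. The cost is a few lines of SAP text and the matching table shell. No new data are needed, and no hypothesis test changes.
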